1.0 Background

[figure not shown]
1.1 Biliary Tract Cancer

Biliary tract cancers (BTCs) include malignant intrahepatic and extrahepatic cholangiocarcinomas, gallbladder and ampullary cancers. It is estimated that 11,420 patients will be diagnosed with BTCs in 2016 in United States.(Siegel, Miller et al. 2016) Globally, both the incidence and mortality from BTCs is increasing with much higher incidences in a few regions. Most patients with BTCs present with unresectable or metastatic disease. Even in patients with resectable disease, the recurrences are frequent. The median survival of patients with advanced BTCs is less than 4.5 months.(Glimelius, Hoffman et al. 1996; Sharma, Dwary et al. 2010) Combination gemcitabine and cisplatin has been established as first line standard of care treatment based on the Advanced Biliary Tract Cancer-02 (ABC-02) phase III trial.(Valle, Wasan et al. 2010) Unfortunately, the median overall survival (OS) was less than a year in this trial. There is no FDA approved second line option for patients with advanced BTCs. There is a huge unmet need to develop novel therapies to improve outcome for patients diagnosed with BTCs.

1.2 FTD/TPI (TAS-102; trifluridine/tipiracil)

[figure not shown]
FTD/TPI (TAS-102; Lonsurf; trifluridine/tipiracil) is a novel oral nucleoside consisting of α,α,α -trifluorothymidine (FTD) and 5-chloro-6-(2-iminopyrrolidin-1-yl) methyl-2,4-(1*H*,3*H*)-pyrimidinedione hydrochloride (TPI) at a molar ratio of 1:0.5. The active antitumor component of FTD/TPI is FTD which inhibits thymidylate synthase and is incorporated into DNA in tumor cells.

Trifluridine, an antineoplastic thymidine-based nucleoside analogue, is described chemically as 2'-deoxy-5-(trifluoromethyl) uridine, and has the following structural formula:

Trifluridine has a molecular formula C10H11F3N2O5 and a molecular weight of 296.20. Trifluridine is a white crystalline powder, soluble in water, ethanol, 0.01 mol/L hydrochloric acid, 0.01 mol/L sodium hydroxide solution; freely soluble in methanol, acetone; sparingly soluble in 2-propanol, acetonitrile; slightly soluble in diethyl ether; and very slightly soluble in isopropyl ether.

Tipiracil hydrochloride, a thymidine phosphorylase inhibitor, is described chemically as 5-chloro-6-[(2-iminopyrrolidin-1-yl)methyl]pyrimidine-2,4-(1*H*,3*H*)-dione monohydrochloride or 2,4(1*H*,3*H*)-Pyrimidinedione, 5-chloro-6-[(2-imino-1-pyrrolidinyl)methyl]-, hydrochloride (1:1), and has the following structural formula:

The clinical efficacy and safety of FTD/TPI was evaluated in an international, randomized, double-blind, placebo-controlled study (RE COURSE study) conducted in patients with previously treated metastatic colorectal cancer (CRC). A total of 800 patients were randomized 2:1 to receive trifluridine/tipiracil (n = 534) plus best supportive care (BSC) or matching placebo (n = 266) plus BSC. Patients received 35 mg/m² trifluridine/tipiracil or matching placebo orally twice daily after meals on Days 1–5 and 8–12 of each 28-day cycle until disease progression or unacceptable toxicity. The primary efficacy outcome measure was overall survival (OS) and an additional efficacy outcome measure was progression-free survival (PFS). Patient demographics and baseline characteristics were similar between groups. The median age was 63 years, 61% were male, and 58% and 35% were White and Asian respectively. The RE COURSE study met the efficacy endpoints of significant improvement in OS and PFS compared to placebo in patients with refractory mCRC whose disease had progressed after standard therapies. The median OS was 7.1 months with FTD/TPI compared to 5.3 months in placebo group (Hazard ratio: 0.68; 95% CI: 0.56-0.78). Median PFS was 2 months in FTD/TPI group and 1.7 months in placebo group (Hazard ratio: 0.48; 95% CI: 0.41-0.57). The objective response rate was 1.6%. Common adverse events included fatigue, nausea, vomiting, diarrhea, anorexia and cytopenias. Table 1 lists the common adverse events associated with FTD/TPI.

Table 1: Adverse events (>5%) in the RE COURSE study occurring more commonly than placebo.

Adverse Events	Trifluridine/tipiracil		Placebo	
	All Grades	Grade 3-4	All Grades	Grades 3-4
Gastrointestinal Disorders				
Nausea	48%	2%	24%	1%
Diarrhea	32%	3%	12%	<1%
Vomiting	28%	2%	14%	<1%
Abdominal Pain	21%	2%	18%	4%
Stomatitis	8%	<1%	6%	0%
General disorders				
Asthenia/fatigue	52%	7%	35%	9%
Pyrexia	19%	1%	14%	<1%
Metabolism and nutrition disorders				
Decrease appetite	39%	4%	29%	5%
Nervous system disorders				
Dysgeusia	7%	0%	2%	0%
Skin and subcutaneous tissue disorders				
Alopecia	7%	0%	1%	0%

Adverse Events	Trifluridine/tipiracil		Placebo	
	All Grades	Grade 3-4	All Grades	Grades 3-4
Blood and lymphatic disorders				
Anemia	77%	18%	33%	3%
Neutropenia	67%	38%	1%	0%
Thrombocytopenia	42%	6%	8%	<1%

1.3 Study Rationale

Fluoropyrimidine-based regimens are frequently utilized for treatment of BTCs despite the fact that they are not FDA approved.(Huggett, Passant et al. 2014; Rogers, Law et al. 2014) On retrospective analysis, fluoropyrimidine based treatments have shown to be associated with improved survival.(Huggett, Passant et al. 2014) However, there are only limited small prospective studies reported utilizing fluoropyrimidines. Single agent 5-fluorouracil has yielded response rates of 10-32% with median OS of approximately 6 months as a first line treatment.(Falkson, MacIntyre et al. 1984; Choi, Choi et al. 2000) Addition of other chemotherapy agents including platinum agents and irinotecan are associated with better response rates at the expense of increase toxicities. However, none of the combination regimens have consistently demonstrated superiority over single agent fluoropyrimidine alone.(Hezel and Zhu 2008) The combination of 5-flourouracil and irinotecan demonstrated a response rate of 10% in a study of 30 patients.(Feisthammel, Schoppmeyer et al. 2007) Another study evaluating the combination of 5-fluorouracil and cisplatin reported response rates of 24% with median survival of 10 months in the first line setting.(Ducréux, Rougier et al. 1998) Capecitabine and cisplatin combination demonstrated median progression free survival ranging from 2.5-3.7 months in untreated advanced BTCs.(Kim, Chang et al. 2003; Hong, Lee et al. 2007) S-1, a combination of tegafur (that is converted to 5-fluorouracil in the liver), 5-chloro-2,4-dihydroxypyridine (inhibitor of dihydropyrimidine dehydrogenase) and potassium oxonate has also shown activity in advanced BTCs as a single agent.(Ueno, Okusaka et al. 2004) These studies suggest there may be a role for fluoropyrimidines in advanced BTCs.

The active antitumor component of FTD/TPI is FTD is incorporated into DNA in tumor cells. FTD has also shown to inhibit thymidylate synthase in tumor xenograft models. The incorporation into DNA is known to have antitumor effects, because inhibition of thymidylate synthase caused by oral FTD rapidly disappears after the drug's elimination. The mechanism of action of FTD/TPI is somewhat dependent on its dosing schedule.(Lenz, Stintzing et al. 2015) Greater inhibition of thymidylate synthase was observed with continuous infusion of FTD than twice daily dosing.(Tanaka, Sakamoto et al. 2014) In contrast, the level of incorporation into DNA was higher with twice-daily oral dosing. Thus, clinically with twice daily dosing schedule of FTD/TPI, incorporation into DNA is the primary mechanism of action for antitumor effects. TPI is a potent inhibitor of thymidine phosphorylase, which is the enzyme that degrades FTD and helps maintain adequate plasma concentration needed for its activity.

The mechanism of FTD/TPI is thus different from single agent fluoropyrimidine and has shown activity in both fluoropyrimidine sensitive and resistant tumors.(Emura, Nakagawa et al. 2004; Emura, Suzuki et al. 2004) The primary mechanism of resistance to 5-fluorouracil seems to be decrease in activity of orotate phosphoribosyltransferase resulting in decrease in cellular uptake of 5-fluorouracil in the RNA fraction.(Murakami, Kazuno et al. 2000) There is no change in the levels of thymidylate synthase. FTD has demonstrated activity in 5-fluorouracil resistant colorectal and gastric cell lines as

activity of FTD/TPI is not dependent upon orotate phosphoribosyltransferase.(Lenz, Stintzing et al. 2015) Autophagy has also shown to play a role in resistance to 5-fluorouracil but not to FTD.(Bijnsdorp, Peters et al. 2010). These studies suggest that FTD/TPI may have better clinical activity in advanced BTCs than fluoropyrimidine alone.

1.4 Study Design

This is the single arm phase II trial to assess the efficacy of FTD/TPI in advanced, refractory BTCs. The primary end point of this study is 16-week progression-free survival. If 30% of patients remain progression-free at 16-weeks, this trial will be considered a success warranting bigger trials. We will accrue 25 evaluable patients using a single stage design. The total sample size of this study is 28 to account for 3 possible non-evaluable subjects.

Patient will receive FTD/TPI at the dose of 35 mg/m² on Days 1-5 and 8-12 of 28-day cycle. Patient will receive treatment until disease progression or unacceptable toxicities. Patients will undergo restaging scans every 2 cycles. Subjects will be monitored for adverse events from the beginning of the study drug to 28 days after the last dose. We will collect blood samples for determination of cell free DNA and circulating tumor cells at baseline, after 2 cycles and at progression.

2.0 Goals

2.1 Primary Goal

Determine the efficacy of FTD/TPI (TAS-102) in patients with refractory cholangiocarcinoma using progression-free survival at 16 weeks.

2.2 Secondary Goals

- 2.21 Assess the safety and tolerability of FTD/TPI (TAS-102) in patients with refractory cholangiocarcinoma through adverse event monitoring.
- 2.22 Further explore the efficacy of FTD/TPI (TAS-102) in patients with refractory cholangiocarcinoma by overall response rates, progression-free survival, and overall survival.

2.3 Correlative Research

- 2.31 Determine if circulating tumor cells (CTCs) or cell-free DNA (cfDNA) at baseline correlates with prognosis or response to therapy.
- 2.32 Determine if change in CTCs or cfDNA correlates with efficacy endpoints.
- 2.33 Determine if different mutational status of the tumor will affect efficacy endpoints.

3.0 Patient Eligibility

3.1 Registration – Inclusion Criteria

3.11 Age \geq 18 years.

3.12 Histological confirmation of advanced biliary tract cancers including cancers originating in gallbladder who have received at least one line of systemic anticancer therapy.
Note: Patients who have either progressed or are intolerant to the prior therapy can be included in this study.

3.13 Measurable disease as defined in [Section 11.0](#).

3.14 ECOG Performance Status (PS) 0 or 1 ([Appendix I](#)).

3.15 The following laboratory values obtained \leq 21 days prior to registration.

- Absolute neutrophil count (ANC) \geq 1500/mm³
- Platelet count \geq 100,000/mm³
- Total bilirubin \leq 1.5 \times upper limit of normal (ULN)
- Aspartate transaminase (AST) or Alanine transaminase (ALT) \leq 3 \times ULN
- Creatinine \leq 1.5 \times ULN

3.16 Negative pregnancy test done \leq 7 days prior to registration, for persons of childbearing potential only.

3.17a Provide written informed consent.

3.17b Willing to return to enrolling institution for follow-up (during the Active Monitoring Phase of the study).

3.17c Willing to provide blood samples for correlative research purposes.

3.2 Registration – Exclusion Criteria

3.21 Any of the following because this study involves an agent that has potential genotoxic, mutagenic and teratogenic effects:

- Pregnant persons
- Nursing persons
- Persons of childbearing potential who are unwilling to employ adequate contraception for at least 3 months after the last dose of the study drug

3.22 Co-morbid systemic illnesses or other severe concurrent disease which, in the judgment of the investigator, would make the patient inappropriate for entry into this study or interfere significantly with the proper assessment of safety and toxicity of the prescribed regimens.

3.23 Immunocompromised patients and patients known to be HIV positive and currently receiving antiretroviral therapy. NOTE: Patients known to be HIV positive, but without clinical evidence of an immunocompromised state, are eligible for this trial.

3.24 Uncontrolled intercurrent illness including, but not limited to, ongoing or active infection, symptomatic congestive heart failure, unstable angina pectoris, cardiac arrhythmia, or psychiatric illness/social situations that would limit compliance with study requirements.

3.25 Receiving any other investigational agent which would be considered as a treatment for the primary neoplasm \leq 21 days prior to registration..

- 3.26 Receiving any anticancer therapy for biliary tract cancer \leq 21 days prior to registration.
- 3.27 Other active malignancy requiring treatment in \leq 6 months prior to registration.
EXCEPTIONS: Non-melanotic skin cancer or carcinoma-in-situ of the cervix.
NOTE: If there is a history of prior malignancy, they must not be receiving other specific treatment for their cancer.
- 3.28 History of myocardial infarction \leq 6 months prior to registration, or congestive heart failure requiring use of ongoing maintenance therapy for life-threatening ventricular arrhythmias.

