4.0 Study Schedules

4.1 Test schedule

Tests and Procedures	Screening prior to registration	Active Treatment			End of Treatment	
		D1 of each cycle	D8 of Cycle 1 only	Every 2 cycles	End of Treatment	Safety follow up: 30 days post treatment
window		±7 days	±3 days	±7 days	±7 days	±7 days
History and exam, Wt, PS	X	X	X		X	X
Height	X					
Adverse event assessment	X	X	X		X	X
Pregnancy test ¹	X					
Hematology: CBC with differential	X	X	X		X	X
Chemistry ²	X	X	X		X	X
CA19-9 ³		X		X ⁴	X	
Tumor imaging - CT (chest, abdomen, pelvis) or CT (chest) and MRI (abdomen, pelvis)	X ⁵			X ⁶	X	
Research blood specimens ^{7,R}		X			X	
Patient Medication Diary (Appendix II) ⁸		X				

Cycle = 28 days; R=Research funded

¹ For persons of childbearing potential only. Must be done ≤7 days prior to registration.

² Chemistry: Na, K, albumin, AST, ALT, alkaline phosphatase, total and direct bilirubin, creatinine

³ Baseline prior to Cycle 1, Day 1, then every two cycles or as clinically indicated

⁴ To be performed ≤7 days prior to planned Day 1 of odd numbered cycles (Cycle 3, 5, 7 etc) or as clinically indicated

⁵ Can be performed ≤28 days prior registration

⁶ To be performed ≤7 days prior to planned Day 1 of odd numbered cycles (Cycle 3, 5, 7 etc) or as clinically indicated

⁷ Research blood specimens to be collected on Cycle 1 Day 1 (or any time between registration and Cycle 1 Day 1), Cycle 3 Day 1 and end of treatment (see [Section 14.0](#))

⁸ The diary must begin the day the patient starts taking the medication and must be completed per protocol and returned to the treating institution

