10.5 Other Required Reporting

10.51 Unanticipated Problems Involving Risks to Subjects or Others (UPIRTSOS)

Unanticipated Problems Involving Risks to Subjects or Others (UPIRTSOS) in general, include any incident, experience, or outcome that meets **all** of the following criteria:

1. Unexpected (in terms of nature, severity, or frequency) given (a) the research procedures that are described in the protocol-related documents, such as the IRB-approved research protocol and informed consent document; and (b) the characteristics of the subject population being studied;
2. Related or possibly related to participation in the research (in this guidance document, possibly related means there is a reasonable possibility that the incident, experience, or outcome may have been caused by the procedures involved in the research); and
3. Suggests that the research places subjects or others at a greater risk of harm (including physical, psychological, economic, or social harm) than was previously known or recognized.

Some unanticipated problems involve social or economic harm instead of the physical or psychological harm associated with adverse events. In other cases, unanticipated problems place subjects or others at increased *risk* of harm, but no harm occurs.

Note: If there is no language in the protocol indicating that pregnancy is not considered an adverse experience for this trial, and if the consent form does not indicate that subjects should not get pregnant/impregnate others, then any pregnancy in a subject/patient or a male patient's partner (spontaneously reported) which occurs during the study or within 120 days of completing the study should be reported as a UPIRTSO.

Mayo Clinic Cancer Center (MCCC) Institutions:

If the event meets the criteria for IRB submission as a Reportable Event/UPIRTSO, provide the appropriate documentation and use the Mayo Clinic Cancer Center Expedited Event Report form

<http://livelcycle2.mayo.edu/workspace/?startEndpoint=MC4158-56/Processes/MC4158-56-Process.MC4158-56>, to submit to

[contact]. The Mayo Regulatory Affairs Office will review and process the submission to the Mayo Clinic IRB.

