10.55 Pregnancy, Fetal Death, and Death Neonatal

If a patient becomes pregnant while in the study, the study treatment must be immediately discontinued. Pregnancy information for a female patient should be reported **within 24 hours** from the time the investigator first becomes aware of a pregnancy or its outcome. This should be performed by completing a Pregnancy Form and faxing it to Taiho Pharmacovigilance or designee.

New and/or corrected information regarding the pregnancy obtained after submitting the initial Pregnancy Form must be submitted by faxing an updated Pregnancy Form to Taiho Pharmacovigilance or designee.

If outcome of the pregnancy is a stillbirth, congenital anomaly/birth defect, or a serious event in the mother, report as an SAE to Taiho Pharmacovigilance or designee.

If a female subject (or female partner of a male subject) taking investigational product becomes pregnant, the subject taking should notify the Investigator, and the pregnant female should be advised to call her healthcare provider immediately. The patient should have appropriate follow-up as deemed necessary by her physician.

NOTE: When submitting Mayo Expedited Adverse Event Report reports for “Pregnancy”, “Pregnancy loss”, or “Neonatal loss”, the potential risk of exposure of the fetus to the investigational agent(s) or chemotherapy agent(s) should be documented in the “Description of Event” section. Include any available medical documentation. Include this form:

http://ctep.cancer.gov/protocolDevelopment/electronic_applications/docs/PregnancyReportFormUpdated.pdf

10.551 Pregnancy

Pregnancy should be reported in an expedited manner as **Grade 3** “**Pregnancy, puerperium and perinatal conditions - Other (pregnancy)**” under the Pregnancy, puerperium and perinatal conditions SOC. Pregnancy should be followed until the outcome is known.

10.552 Fetal Death

Fetal death is defined in CTCAE as “A disorder characterized by death in utero; failure of the product of conception to show evidence of respiration, heartbeat, or definite movement of a voluntary muscle after expulsion from the uterus, without possibility of resuscitation.”

Any fetal death should be reported expeditiously, as **Grade 4** “**Pregnancy, puerperium and perinatal conditions - Other (pregnancy loss)**” under the Pregnancy, puerperium and perinatal conditions SOC.

10.553 Death Neonatal

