10.83 Pregnancy

If a patient becomes pregnant while in the study, the study treatment must be immediately discontinued. Pregnancy information for a female patient should be reported **within 24 hours** from the time the investigator first becomes aware of a pregnancy or its outcome. This should be performed by completing a Pregnancy Form and faxing it to Taiho Pharmacovigilance or designee.

New and/or corrected information regarding the pregnancy obtained after submitting the initial Pregnancy Form must be submitted by faxing an updated Pregnancy Form to Taiho Pharmacovigilance or designee.

If outcome of the pregnancy is a stillbirth, congenital anomaly/birth defect, or a serious event in the mother, report as an SAE to Taiho Pharmacovigilance or designee.

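### The only contraception criterion (exclusion 3.21) does not reach male patients whose partner can become pregnant

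*Combined protocol and SAP*

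**What the plan says.** Item 3.21 in section 3.2 lists three groups to exclude and gives one reason for all of them: "this study involves an agent that has potential genotoxic, mutagenic and teratogenic effects". The first two groups are pregnant and nursing persons. The third is "Persons of childbearing potential who are unwilling to employ adequate contraception for at least 3 months after the last dose of the study drug". No other eligibility criterion mentions contraception, and neither do the treatment sections or the drug information in section 15.

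The term in the third bullet appears in two other places. Inclusion 3.16 requires a negative pregnancy test "for persons of childbearing potential only". Footnote 1 of the test schedule in section 4.1 says of the same test: "For persons of childbearing potential only. Must be done ≤7 days prior to registration".

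The safety sections go further than the eligibility section. The note in 10.51 sets a default reporting rule for "any pregnancy in a subject/patient or a male patient's partner (spontaneously reported) which occurs during the study" or within 120 days of completing the study. One of its conditions is "if the consent form does not indicate that subjects should not get pregnant/impregnate others". Section 10.55 addresses the event directly: "If a female subject (or female partner of a male subject) taking investigational product becomes pregnant", the subject is to notify the investigator and the pregnant woman is to contact her own healthcare provider. For patients themselves, 10.83 says: "If a patient becomes pregnant while in the study, the study treatment must be immediately discontinued".

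**The concern.** An exclusion criterion decides who may enter the trial, and sites apply it as written. Here the group it names looks narrower than the reason given for it. Teratogenic potential bears most directly on a patient who may carry a pregnancy. Genotoxic and mutagenic potential is not, on its face, confined to such patients. The protocol also expects that a male patient's partner may become pregnant, because it says what to do when that happens. What is missing from the text is a step before that event.

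At stake is exposure of a partner's pregnancy that an eligibility rule could have helped to prevent. The trial's efficacy conclusion is not at stake.

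**Working it through.** The plan states no figure on this point and no arithmetic applies. The check is to read together every section that deals with contraception, childbearing potential, pregnancy or a male patient's partner.

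1. **Who does the bullet cover?** Its subject is persons of childbearing potential. The protocol text available gives no separate definition, so the meaning has to come from use. In 3.16 and in footnote 1 of section 4.1 the term marks those who must have a pregnancy test. If it included men, both places would require men to be tested for pregnancy. The consistent reading is patients who can themselves become pregnant.

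2. **Does another criterion fill the gap?** Exclusions 3.22 and 3.24 concern comorbid and uncontrolled illness, and neither touches contraception. Inclusions 3.17a to 3.17c concern consent, return for follow-up and blood samples. None reaches an unwilling male patient.

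3. **Does the reason for the bullet stop at patients who can become pregnant?** The lead-in names three properties of the drug. At least two of them, genotoxic and mutagenic potential, are stated without that limit. Section 1.3 also gives incorporation into DNA as the main mechanism of action under twice-daily dosing.

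4. **Does the protocol treat partner pregnancy as relevant?** Yes, in 10.51 and 10.55. The first is a conditional reporting rule. The second has the subject notify the investigator and the pregnant woman seek care. Both act once a pregnancy has occurred, and neither asks a male patient to prevent one.

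5. **Result.** A man who declines contraception and whose partner can become pregnant meets no exclusion in section 3.2. Section 6.2 has the registration system verify eligibility, and on these criteria he would pass.

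6. **The period named.** Read literally, the third bullet mentions only the time after the last dose. The ordinary reading is that contraception runs through treatment and continues for at least 3 months afterwards. The entry pregnancy test and the order in 10.55 and 10.83 to stop treatment on pregnancy both support that reading. This is a matter of wording only.

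**The case against.** The strongest reply is that the consent form was not available, and its absence here does not mean the plan lacks it. Section 10.51 treats the consent form as a place to tell subjects not to become pregnant or impregnate others. Section 10.2 says the form may carry study-specific information that is not in the protocol. An instruction to men could well sit there. This stands, and it makes any harm conditional. It does not change what the criterion says, and the criterion and the consent form should agree.

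A second reply is that 3.21 is coherent as a list about patients who are, or may become, pregnant or nursing. Applying its reason to men then needs a premise about harm through the male patient, and section 15 gives no reproductive-toxicity data to supply one. This stands in part. The gap is not an internal contradiction. It is a reasonable extension of the sponsor's own words on genotoxic and mutagenic potential, supported by the attention that 10.51 and 10.55 give to partners.

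Three stronger readings are tempting, and the documents support none of them:

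- A reader might infer that men in this trial receive no contraception advice. The consent form could show otherwise.
- A reader might infer that contraception is not required during dosing. No investigator would plausibly apply the bullet in that way, for the reasons in the last step of the working.
- A reader might take the 14 men among 28 expected patients in section 16.73 as the number at risk. That figure is only the planned split by sex. The documents do not say how many men would have a partner who can become pregnant.

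**Conclusion.** The concern holds as a cheap patient-safety improvement of minor weight. The only contraception criterion in the protocol text available leaves out male patients with a partner who can become pregnant, so a man unwilling to use contraception is eligible as written. No number of affected patients can be given. The sample size, the 16-week endpoint, the decision rule and the analysis are unaffected.

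The conclusion rests on two assumptions: that the term in 3.21 has the same meaning as in 3.16 and footnote 1, and that genotoxic and mutagenic potential is a reason for caution in men too. If the consent form already instructs men, what remains is to bring the written criterion into line with it.

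**What to change.** Amend the third bullet of 3.21 in two places:

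- After the opening reference to persons of childbearing potential, add *and male patients with partners of childbearing potential*.
- Before the post-treatment interval, add *during study treatment and*. This clarifies the wording and adds no new requirement.

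The interval of at least 3 months would then also apply to men. For them it is an assumption carried over from the existing bullet, because the documents give no source for a male interval. The 120 days in 10.51 is a reporting window counted from completing the study, so it does not supply one. The sponsor should confirm the interval against the label or the investigator's brochure before the amendment is issued, and check that the consent form says the same.

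The cost is one sentence in an amendment and a check of the consent form, with no extra patients, visits or tests. The downside is that a few candidates may decline or become ineligible.
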